6.8 Minimization of Bias

Subject selection, subject treatment, and the evaluation of study data are sources of bias. Efforts to minimize potential bias include, but are not limited to:

- Prior to enrollment, rigorous screening will be performed to confirm enrollment eligibility with defined inclusion and exclusion criteria.
- Baseline characteristics and medical history will be collected to statistically access possible characteristics that may influence study endpoints.
- All clinical study site personnel and sponsor/delegate personnel will be thoroughly trained on their respective aspects of the clinical study.
- All Investigators will be trained on and required to follow the Clinical Investigational Plan (CIP)/protocol.
- Monitoring visits will be undertaken to verify eCRFs against source data and compliance with the CIP/protocol.
- An independent clinical events adjudication reviewer will regularly review and adjudicate adverse events and deaths.
- A centralized evaluator will be used to describe atrial arrhythmia data received from the continuous ECG monitor.

6.9 Subject Withdrawal

Individual subjects may withdraw their consent to participate in the study at any time. An Investigator may discontinue a subject's participation in the study at any time to protect the safety, rights, or welfare of the subject.

Subjects missing follow-up visits will not be considered lost to follow-up (LFU) until adequate attempts to contact the subject have been made. The Investigator or designee will attempt to contact a subject at least 3 times prior to designating them as lost to follow-up; 1 of these 3 attempts should include contacting the subject via certified mail. A Study Exit eCRF form will be completed when a subject is lost to follow-up.

7 CLINICAL STUDY TREATMENTS AND FOLLOW-UP VISITS

7.1 General Overview

The clinical study is a single-arm evaluation of subjects diagnosed with cavotricuspid isthmus dependent typical atrial flutter. All subjects will undergo ablation of the cavotricuspid isthmus (CTI) for the treatment of typical atrial flutter.

7.2 Informed Consent

It is the responsibility of the Investigator (or designee) to give each subject full and adequate verbal and written information regarding all aspects of the study procedure, device, and associated risks. A signed ICF must be obtained from the subject before any study procedures not considered standard of care (SOC) for an AFL ablation are undertaken. The informed consent form (ICF) must be signed by the subject and witnessed by the Investigator (or designee). The original signed ICF is filed in the subject's study records with one copy placed in the subject's medical notes and one copy provided to the subject.

7.3 Subject Screening

The following information should be collected to verify eligibility in the clinical study:

- Review of all inclusion/exclusion criteria to confirm subject eligibility
- Subject demographics
- Medical history review including:
 - Information specific to the exclusion criteria
 - History of atrial fibrillation
- Physical examination (at a minimum Cardiovascular, Respiratory, Extremities should be evaluated)
- Vital signs
- 12-lead ECG documenting episode of cavotricuspid dependent typical atrial flutter within 180 days (6-months) of enrollment
- Subject symptoms
- Current cardiovascular and anticoagulation medications

7.4 **Baseline Evaluation**

The following information should be collected at baseline and reviewed prior to the ablation procedure:

- TTE within 90 days of procedure (if needed)
- 12-lead ECG
- Pregnancy test for women of childbearing potential within 7-days prior to the study procedure following the institution's SOC

7.5 Ablation Pre-Procedure Requirements

[figure not shown]
7.5.1 Atrial Thrombus

No procedure should be completed if there is any evidence of atrial thrombus. The method of thrombus assessment should be recorded on the Procedure eCRF.

7.5.2 Anticoagulation and Atrial Thrombus Assessment

Periprocedural anticoagulation and pre-procedure assessment for atrial thrombus should follow the 2019 AHA/ACC/HRS Focused Update of the 2014 AHA/ACC/HRS Guideline for the Management of Patients With Atrial Fibrillation and the 2017 HRS/EHRA/ECAS/APHRS/SOLAECE expert consensus statement on catheter and surgical ablation of atrial fibrillation

- A transesophageal echocardiogram is required for all subjects with atrial flutter for \geq 48 hours or unknown duration AND the subject has not been anticoagulated with a vitamin K antagonist or NOAC for at least 21 days before the study procedure.
 - A transesophageal echocardiogram for subjects with atrial flutter less than 48 hours duration prior to study procedure may be performed at the investigators discretion but is not mandatory.
- Subjects who are required to have a transesophageal echocardiogram, should have one performed within 24 hours of the study procedure.
- Any subject who is determined to have cardiac thrombus will not undergo the study procedure and will be exited from the study.

Transesophageal Echocardiogram Requirement Flow Chart

7.5.3 Antiarrhythmic Medications

To minimize the impact of oral antiarrhythmic drugs (AADs), on device effectiveness, Class I/III AADs should be discontinued at least 5 half-lives (Table 7) prior to the ablation procedure.

Antiarrhythmic Medication	5 Half-lives
Class I	
Lidocaine	7.5-10 hours
Procainamide	15-20 hours
Propafenone	15 hours- 2 days
Class III	
Amiodarone*	120 days

Table 7. Antiarrhythmic Medication 5 half-lives

Dronedarone	5 days
Sotalol	2-4 days
Ibutilide	12 hours-2.5 days

*Exclusion Criteria #6: Administration of oral amiodarone within 120 days prior to procedure excluding a one-time IV/oral administration of ≤ 2000 mg in a 24-hour period.

7.5.4 Subject Preparation

Subjects will be prepped and draped for the ablation procedure following standard hospital practice. This includes placement of all cables/patches used for ECG monitoring and operation of all devices to be used during the procedure.

7.5.5 Anesthesia

Use of conscious sedation or general anesthesia will follow the Investigator preferences as directed by the subject's health status.

7.5.6 AcQBlate Force System Set-Up

The AcQBlate Force System including the AcQBlate FORCE catheter, the Qubic RF Generator, the Qiona Irrigation Pump, Tubing Set, and assorted cables should be prepared and connected following the IFU and Investigator training. During the procedure, Acutus Medical personnel will be available to provide onsite training on any aspects of the AcQBlate Force System set-up and operation.

7.6 CTI Ablation Procedure

7.6.1 Confirmation of Conduction through the CTI

Entrainment pacing from the cavotricuspid isthmus during atrial flutter will be attempted prior to initiating RF ablation to verify that the CTI is part of the arrhythmia circuit. When clinically reasonable, the investigator may attempt to induce atrial flutter using pacing maneuvers when the subject presents to the lab in sinus rhythm.

Documentation of concealed entrainment should be printed and recorded on the appropriate eCRF.

If Investigator is unable to induce and entrain CTI dependent AFL, the Investigator may choose to confirm and document conduction through the CTI. CTI conduction must be confirmed prior to initiating RF ablation. Documentation of inability to induce and/or entrain should be printed and recorded on the appropriate eCRF. Confirmation of conduction through the CTI should be demonstrated using pacing maneuvers.

Documentation of conduction through the CTI should be printed and recorded on appropriate CRF.

If CTI dependent AFL cannot be confirmed or CTI conduction cannot be confirmed, the subject will be considered an ITT failure subject and exited from the study at the 7-day follow-up visit.

If during inducement, entrainment, or other pacing maneuvers the subject is paced into AF, DCCV may be performed to attempt conversion to sinus rhythm so the CTI conduction measurement may proceed. If the investigator determines further ablation beyond the CTI is warranted the subject will be exited from the study after being followed for 7-days for safety.

The AcQBlate FORCE catheter shall not be used to initiate ablation procedure until conduction through the CTI is confirmed.

7.6.2 Ablation Considerations

In order to reduce the risk of complications the following measures need to be considered for ablation of the atria. Recommended ablation target values are identified in Table 8 below.

- Titrate the energy, starting with an initial power of ≤ 25 W. Do not exceed 30 W.
- If a transmural lesion is not achieved, defined by 70% 80% reduction of the intracardiac electrogram (IEGM) signal or emergence of double potentials of equal and low amplitude, after 20 seconds the energy may be increased but not in excess of 40 W. Ablations at 31-40 W should not exceed 15 seconds in duration.
- Avoid excessive ablation durations at any focal location. If focal ablations are applied, duration of RF power at one location requires careful attention to commonly used ablation effectiveness parameters such as electrogram amplitude reduction, electrogram morphology change or impedance changes.
- Avoid excessive contact force while using a steerable sheath to guide the ablation catheter.
- Optimal contact force is 3-20 g. Do not exceed 40 g for prolonged periods.
- Do not increase power only because no or little temperature increase is measured by the AcQBlate FORCE and the Biotronik Qubic RF ablation generator. The tip of the AcQBlate FORCE has good cooling properties to avoid thrombus formation. The displayed temperature reflects the temperature of the irrigated electrode, not of the tissue.
- Irrigation flow rate must follow the IFU.
- Use of half-normal saline is not allowed.

Parameter	Value	Value
Power Range*	10 to 30 Watts	31 to 40 Watts
Irrigation flow rate during RF application	8 ml/min	15 ml/min
RF Ablation Energy Delivery**	< 60 seconds	< 15 seconds
Temperature monitoring during RF application***	itoring during RF application*** 40° - 50° C	
Contact Force Range	3 grams to 20 grams	

Table 8. Recommended Target Values for Ablation

* It is recommended that lower power levels be used and titrated up to 40W when clinically effective ablation cannot be achieved at lower energy levels and within the contact force range. Maximum power must not exceed 40W. Note that high power levels increase the risk of steam pops, perforation, char, coagulum and/or extracardiac damage, especially when applied to the posterior wall. Impedance drops, electrogram reduction and/or electrogram morphology change may be used to guide RF termination.

** Maximum duration of ablation applies to the duration of RF ablation energy delivery at the same location. Duration of ablation as well as the decision to interrupt RF power delivery at any time during RF ablation should be guided by the clinical judgement of the investigator and monitoring of commonly used ablation effectiveness parameters such as electrogram amplitude reduction, electrogram morphology change or impedance changes.

*** The temperature displayed on the RF generator is not representative of the tissue temperature or the temperature of the electrode-tissue interface.

Warning: Higher contact forces may not improve the characteristics of lesion formation and may increase the risk for perforation during manipulation of the catheter.

7.6.3 CTI Ablation

Ablation of the CTI using the investigational device should follow the Investigator's standard of care. Use of a deflectable long vascular sheath to achieve catheter stability is encouraged. Pacing from the CS during the ablation is at the discretion of the Investigator. Power and irrigation flow setting should follow Table 8. Ablation beyond the CTI is not allowed. No left sided ablations are allowed.

7.6.4 Confirmation of Bidirectional Block

Initial bidirectional block (BDB) confirmation should meet the study endpoint definition of:

• Demonstration of bidirectional electrophysiological conduction block through the cavotricuspid isthmus (CTI) using both coronary sinus ostium (CS) and annular low right atrial pacing maneuvers.

This acute endpoint should be re-confirmed at least 20-minutes following the last RF ablation with the investigational device. If recovery of isthmus conduction occurs, additional ablations should be performed at the site of the reconnection, and the confirmation/reconfirmation steps must be repeated. A reset of the 20-minute wait time for reconfirmation is required. A second investigative catheter or alternate catheter curve may be used prior to designation as ablation failure. Maximum RF time before considering a non-investigational catheter is at the discretion of the Investigator but shall not exceed 60 minutes of RF time. If the Investigator is unable to achieve bidirectional block with the investigational catheter(s), it is recommended, at the Investigator's discretion, to use a commercially available ablation catheter approved for typical atrial flutter to complete the procedure.

7.7 **Post Ablation Recovery**

At the conclusion of the procedure, the subject should be recovered following the Institution's standard practice. Sheath removal may be completed when acceptable hemostasis can be achieved. The use of protamine to reverse anticoagulation is at the discretion of the Investigator. Protamine use will be recorded on the Procedure eCRF.

7.8 Procedure Data Collection

Collection of data generated as a result of the procedure should include:

- Print out of 12-lead ECG at procedure start
- Print out of intracardiac AFL
- Print out of entrainment pacing results pre-ablation for the CTI
- Print out of attempts to prove conduction through the CTI
- Print out of 12-lead ECG at end of procedure
- Demonstration of initial BDB
- Demonstration of BDB 20 minutes following initial determination
- Total procedure time (from first venous access to last cardiac catheter removed)
- Total ablation time for CTI ablation
- Total fluoroscopy time for the CTI ablation procedure
- Cumulative irrigation volume for CTI ablation
- Pre-set parameters for RF power and temperature
- Maximal parameters for RF power and temperature for CTI ablation
- Number of RF applications for CTI ablation

- Cross over of any non-investigational catheter (including reason for change out)
- Recording of all IV cardiac medications and anticoagulation infused during the procedure
- Usability characteristic data will be collected.
- Device identification

7.8.1 Post Ablation Recovery

Post ablation recovery and removal of the introducer sheaths should follow the institution's standard of care.

7.8.2 Post Ablation Antiarrhythmic Use

Following the ablation procedure, Investigators are encouraged to discontinue all Class I/III AADs. If continuation of an AAD is clinically indicated, it must be discontinued at least 5 half-lives (Table 10) prior to the 30-day arrhythmia assessment. Changes in any AAD medication will be recorded on the concomitant medication eCRF.

7.8.3 Post Ablation Anticoagulation Use

Due to the potential of atrial stunning following conversion from AFL to SR and to prevent the risk of thromboembolic events, it is recommended that therapeutic anticoagulation be given for at least four (4) weeks with all subjects that presented with pre-ablation AFL of \geq 48-hours. All anticoagulation medications will be recorded on the concomitant medication eCRF.

7.8.4 Hospital Discharge

The following evaluations must be completed prior to discharge (see Table 12):

- Arrhythmia History since the procedure
- Physical Exam (at a minimum Cardiovascular, Respiratory, Extremities should be evaluated)
- Vital Signs
- Symptoms
- Medications
- Adverse Events
- 12-lead ECG *Note: in the event that post-procedure 12-lead ECG documented sinus rhythm*

AND post-procedure 12-lead ECG was taken ≤ 6 hours from discharge, the post-procedure 12-lead ECG may be used to satisfy this requirement.

Careful attention should be placed in the identification of potential cardiac effusions and post-procedure cardiac tamponade. Unexplained reduction in blood pressure, chest pain or shortness of breath may require a post-procedure Transthoracic Echo (TTE) and further evaluation and management as indicated.

7.9 Follow-up Visits

Screening, procedure, and follow-up visits are outlined in Table 9.

All treatment subjects will have data collected at screening, procedure, hospital discharge, 7and 30-days post procedure. The table below outlines the procedures and testing performed while enrolled in the clinical study.

 Table 9. Schedule of Events

Study Activities	Screening & Baseline	Ablation Procedure	Pre-Discharge	7-Days (± 3-days Phone call)	30-Days (± 7-days)	Unscheduled Follow-up*
Informed Consent	Х					
Medical History & Physical Exam	X		X		X	X
Medications	Х	Х	X	X	Х	X
Transthoracic Echo (TTE) (if needed)	X Within 90 days of index procedure					
Thrombus Assessment: Transesophageal Echocardiogram (TEE) **		X				
Adverse Events		Х	X	X	X	X
Symptom History	X		X	X	X	X
12-lead ECG	X	X	X		X	X
24-hour Holter or patch monitor					X	X
SOC Pre-procedure Labs	X					
Pregnancy Test (female subjects of childbearing age)	X					

*Only required if subject reports symptoms associated with cardiac arrhythmia or in the case of a procedure related adverse event

**A transesophageal echocardiogram is required for all subjects with atrial flutter for \geq 48 hours or unknown duration AND the subject has not been anticoagulated with a vitamin K antagonist or NOAC for at least 21 days before the study procedure. Subjects who are required to have a transesophageal echocardiogram, should have one performed within 24 hours of the study procedure (reference section 7.5.2)

Acutus Medical, Inc.

7.9.1 7-Day Follow-up Visit

Subjects will be contacted by phone by the clinical study team at 7-days $(7 \pm 3$ -days) following their discharge from the hospital. Information regarding their groin access site(s) and sense of any irregular heart rate must be obtained. If, during the phone discussion any concerns arise that suggest AEs, at the Investigator's discretion, the subject may be asked to return to clinic for a thorough evaluation.

The following evaluations will be performed during the telephone follow-up visit. Data will be recorded on the Follow-Up Visit eCRF.

- Medication history
- Symptoms
- Adverse events assessment

7.9.2 **30-Day Follow-up Visit**

Subjects will be seen in the study center clinic 30-days (30 ± 7 -days) post ablation.

The following evaluations will be performed during the clinic follow-up visit. Data will be recorded on the Follow-Up Visit eCRF.

- Physical exam (at a minimum Cardiovascular, Respiratory, Extremities should be evaluated)
- Vital signs
- Medication history
- Symptoms
- Adverse events assessment
- 12-lead ECG
- 24-hour Holter or patch monitor

7.9.3 Unscheduled Visits

Any visit outside of the scheduled follow-up visit windows will be considered an unscheduled visit. All pertinent data will be recorded on the Follow-up Visit eCRF.

8 STATISTICAL METHODS

8.1 Assumptions for Statistical Analysis

The following assumptions were used in the calculation of sample size:

Endpoint	Literature Based Control	Statistical Margin	Performance Goal	Acutus Estimate	(90% Power α 0.050)
Primary Safety	97.0%	5.5%	93.0%	98.5%	110
Primary Efficacy	93.7%	10%	83.7%	93.7%	85

8.2 Statistical Methods for Safety Evaluation

The primary safety endpoint, the proportion of mITT and select ITT subjects who are free from device/procedure related SAE that occur through 7-days post ablation procedure, will be analyzed using a binomial proportion test. Subjects who do not have evidence of a SAE/SADE from the composite list of safety events will be considered a success.

8.2.1 Primary Safety Endpoint Hypothesis

The null and alternate hypotheses for primary safety endpoint are as follows:

Ho: The proportion subjects in the mITT and select ITT subjects (ρ) who are free from device/procedure related SAE through 7-days post ablation procedure is less than or equal to 93.0%.

Ho:
$$\rho \le 93.0\%$$

Ha: The proportion subjects in the mITT and select ITT subjects (ρ) who are free from device/procedure related SAE through 7-days post ablation procedure is greater than 93.0%.

Ha:
$$\rho > 93.0\%$$

The null hypothesis will be rejected if the one-sided 95% Clopper-Pearson Exact lower confidence bound is greater than 93.0%.

8.2.2 Other Safety Analyses

Individual procedure-device related SAEs at 7-days will be analyzed by event frequencies and proportions of subjects. Total and individual non-serious procedure-device AEs at 30-days will also be analyzed by event frequencies and proportion of subjects. Adverse events will be analyzed in terms of their severity, action taken, and duration to resolution.

Device Deficiency Reports will be analyzed for frequencies of safety events and proportion of subjects as part of the safety analyses.

8.3 Statistical Methods for Efficacy Evaluation

The primary efficacy endpoint, the proportion mITT subjects (β) demonstrating bidirectional block (BDB) of the CTI confirmed at 20 minutes following the last right atrial radiofrequency (RF) application using the investigational catheter, will be analyzed using a binomial proportion test.

8.3.1 Primary Efficacy Endpoint Hypothesis

The null and alternate hypotheses for primary efficacy endpoint are as follows:

Ho: The proportion of mITT subjects (β) demonstrating bidirectional block (BDB) of the CTI confirmed at 20 minutes following the last right atrial radiofrequency (RF) application using the investigational catheter is less than or equal to 83.7%.

Ho:
$$\beta \leq 83.7\%$$

Ha: The proportion of mITT subjects (β) demonstrating bidirectional block (BDB) of the CTI confirmed at least 20 minutes following the last right atrial radiofrequency (RF) application using the investigational catheter is greater than 83.7%.

Ha:
$$\beta > 83.7\%$$

The null hypothesis will be rejected if the one-sided 95% Clopper-Pearson Exact lower confidence bound is greater than 83.7%.

8.4 Study Success Criteria

The study success criteria is defined as the rejection of the null (Ho) hypotheses for safety and efficacy as defined in sections 8.2.1 and 8.3.1, respectively.

• Safety Ho: The proportion subjects in the mITT and select ITT subjects (ρ) who are free from device/procedure related SAE through 7-days post ablation procedure is less than or equal to 93.0%.

Ho:
$$\rho \le 93.0\%$$

Efficacy Ho: The proportion of mITT subjects (β) demonstrating bidirectional block (BDB) of the CTI confirmed at 20 minutes following the last right atrial radiofrequency (RF) application using the investigational catheter is less than or equal to 83.7%.

Ho:
$$\beta \le 83.7\%$$

8.5 Primary Endpoints Sensitivity Analysis

Acutus Medical, Inc. and participating investigators will exercise their best efforts to ensure subjects are not lost to follow-up and that there is a minimal amount of missing data. However, it is recognized that some degree of missing data may exist. To address the potential impact of any such missing data, sensitivity analyses of the primary safety and efficacy endpoints will be performed using the mITT and select ITT Cohorts.

8.6 Primary Endpoints Subgroup Analysis

Subgroup analyses of the primary safety and efficacy endpoints are exploratory. No labeling claims are planned. A Pearson chi-squared test will be performed for any significant differences between gender, ethnicity, race and individual co-morbidities and using a logistic regression test for age.

8.7 Secondary Endpoints

There are no secondary endpoints established for this study.

8.8 Study Sample Size Rationale

The sample size requirement for this protocol was determined using the Statistical Analysis System (SAS) Software (Cary, NC) Proc Power one sample proportion using a normal-approximate z test, with at least 90% power and a one-sided 5% significance level.

For the primary safety endpoint, assuming an estimated primary safety rate of 97% and a null hypothesis proportion of 93%, a minimum sample size of 110 subjects is required.

For the primary efficacy endpoint, assuming an estimated primary efficacy rate of 93.7% and a null hypothesis proportion of 83.7%, a minimum sample size of 85 subjects is required.

Therefore, the minimum required sample size for this study will be 110 subjects. A maximum of 120 mITT subjects will be enrolled.

8.9 Statistical Methods for Baseline, Screening, Procedural Experience and Hospital Discharge Data

Demographics, baseline data, including but not limited to relevant descriptors from the medical history, co-morbidities and medications, will be summarized.

Procedural data collection will also be analyzed and summarized.

Continuous variables are summarized as means, standard deviations, medians, and ranges. Categorical variables are summarized as frequencies and percentages. By-Subject listings of baseline and procedural data will be provided.

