Of the SSEDs listed in Table 1, none provided a comprehensive, tabular summary of SAEs that corresponds with the composite list used for the statistical analysis of the primary safety endpoint of the AcQForce Flutter clinical study. The TOCCATTA trial²¹ was the first multicenter, randomized, controlled trial that used direct contact force in human subjects. The overall event rate for right sided ablations was 2.3%. A comparison of reported events within the SSEDs and the TOCCATTA trial to the pre-defined composite safety definitions suggests an approximate SAE mean event rate of 3.0%, and a weighted mean of 2.9% (Table 2). Note that rates reported in individual studies varied between 2.1% and 5.3%. To account for any differences between the AcQForce Flutter study's primary safety endpoint compared to the previous studies used in the meta-analysis, a derived safety event rate of 3% is expected. Based on this, a performance goal is proposed based on an expected rate of 98.5% and a 5.5% statistical margin. This will define the safety population sample size to support a primary safety endpoint with at least 90% power for the planned sample size.

		Acutus Pre-defined SAE								
Device Trade Name (PMA Number)	N	Death	Cardiac perforation / Pericardial Tamponade	Cerebral Infarct or Systemic Embolism	Myocardial Infarct	Major Access Site Complication	Major Bleeding requiring transfusion	Complete Heart Block	Other Device related SAEs / SADEs	Estimated Safety Event Rate
NaviStar [™] DS 8 mm Deflectable Diagnostic Ablation Catheter Celsius [™] DS 8 mm Deflectable Diagnostic Ablation Catheter Stockert 70 RF Generator (model 87001 with software version 001/033) Catheter Interface Cables (models D- 1195 and D-1170) (P010068)	182	Not Specified	Not Specified	Not Specified	Not Specified	1 (0.5%)	Not Specified	1 (0.5%)	2 (1.1%)	2.2%
IBI Therapyr [™] Dual 8 [™] Ablation Catheter IBI-1500T6 (USA) Cardiac Ablation Generator (P040042)	150	Not Specified	Not Specified	Not Specified	1 (0.6%)	Not Specified	Not Specified	Not Specified	7 (4.7)	5.3%
Therapy Cool Path Duo™ Ablation Catheter Safire BLU Duo™ Ablation Catheter 1500T9-CP Vi.6 Cardiac Ablation Generator (P110016)	188	1 (0.5%)	Not Specified	Not Specified	Not Specified	Not Specified	Not Specified	Not Specified	3 (1.6%)	2.1%
Therapy [™] Cool Flex [™] Ablation Catheter (P110016/ S008)	179	1 (0.6%)	Not Specified	1 (0.6%)	Not Specified	Not Specified	Not Specified	Not Specified	2 (1.1%)	2.2%

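### Section 8.8 sizes with a z test but an exact bound decides: 85 gives 83.3% efficacy power, and 110 for safety fits a 98.5% rate, not the printed 97%

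*Combined protocol and SAP*

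**What the plan says.** Protocol 8.8 names the sizing tool as SAS "Proc Power one sample proportion using a normal-approximate z test, with at least 90% power and a one-sided 5% significance level". It then gives two minima.

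- Safety: "assuming an estimated primary safety rate of 97% and a null hypothesis proportion of 93%, a minimum sample size of 110 subjects is required".
- Efficacy, at an assumed 93.7%: "a null hypothesis proportion of 83.7%, a minimum sample size of 85 subjects is required".

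It concludes: "Therefore, the minimum required sample size for this study will be 110 subjects". It also allows up to 120 mITT subjects.

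The decision rules are exact. Protocol 8.2.1 (safety): "The null hypothesis will be rejected if the one-sided 95% Clopper-Pearson Exact lower confidence bound is greater than 93.0" (per cent). Protocol 8.3.1 (efficacy): "The null hypothesis will be rejected if the one-sided 95% Clopper-Pearson Exact lower confidence bound is greater than 83.7" (per cent). SAP 5.6.1.1 and 5.6.2.1 repeat both rules.

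The safety rate differs between sections. In 3.2, "a performance goal is proposed based on an expected rate of 98.5% and a 5.5% statistical margin". The table in 8.1, introduced by "The following assumptions were used in the calculation of sample size", shows 97.0% as the literature control, 98.5% as the sponsor's estimate, a goal of 93.0% and N = 110. Section 6.4.1 promises 90% power or more for each primary endpoint.

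**The concern.** There are two separate faults in one short section.

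First, the sample size comes from one test and the decision from another. The Clopper-Pearson bound is conservative, and its power moves in steps with the number of failures allowed. A sample size from a smooth normal approximation can therefore fall just short of the size at which one more failure is allowed.

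Second, the safety rate printed in 8.8 is the one that 8.1 labels as the literature control, not the one labelled as the sponsor's estimate. Section 3.2 says that safety drives the sample size, so this rate supports the whole trial. If 97% is really the planning assumption, the trial has little better than an even chance of meeting its safety goal. If 98.5% is the assumption, the trial is adequately sized and 8.8 is misprinted. As written, the reader cannot tell which from 8.8.

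**Working it through.** **Inputs.** One-sided alpha 0.05 and power 0.90 (8.8). Efficacy: p0 = 0.837, p1 = 0.937 (8.1, 8.8). Safety: p0 = 0.93, with p1 = 0.985 (3.2, 8.1) or 0.97 (8.8).

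**Step 1: reproduce the plan's figures with its own z test.**

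n = [(1.645·√(p0(1−p0)) + 1.2816·√(p1(1−p1))) / (p1−p0)]²

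| Endpoint | Numerator | Divided by | n | Rounded up | Plan |
|---|---|---|---|---|---|
| Efficacy, 93.7% vs 83.7% | 0.6076 + 0.3114 | 0.100 | 84.4 | 85 | 85 |
| Safety, 98.5% vs 93% | 0.4197 + 0.1558 | 0.055 | 109.5 | 110 | 110 |
| Safety, 97% vs 93% | 0.4197 + 0.2186 | 0.040 | 254.6 | 255 | 110 |

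So 85 reproduces, and 110 reproduces only at 98.5%. Other variance choices, a continuity correction, the arcsine form and two-sided alpha were tried at 97%. They gave 156 to 428, none near 110. The z-test power of 110 at 97% is 50.0%.

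**Step 2: apply the planned decision rule.** For each n, find the largest number of failures k for which the 5th percentile of Beta(n−k, k+1), which is the Clopper-Pearson lower bound, exceeds p0. Then power = P(X ≤ k) with X ~ Bin(n, 1−p1), and the true type I error is the same sum with 1−p0.

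**Efficacy at 93.7%**

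| n | Failures allowed | Exact power | Type I error |
|---|---|---|---|
| 85 | 7 | 83.3% | 0.024 |
| 86 | 8 | 90.8% | 0.047 |
| 87 | 8 | 90.3% | 0.043 |
| 88 to 92 | 8 | 89.8% falling to 87.4–87.5% | – |
| 93 | 9 | 93.2% | 0.049 |
| 110 | 11 | 95.5% | 0.042 |
| 120 | 12 | 96.0% | 0.035 |

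At 85, eight failures (77/85) give a lower bound of 83.66%, just under 83.7%, so the eighth failure is not allowed. The z rule would accept it: power would be 91.3%, but the true type I error would be 0.051. The first n that reaches 90% is 86, and power is 90% or more at every n from 93.

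**Safety**

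| n | Failures allowed | Power at 97% | Power at 98.5% |
|---|---|---|---|
| 108 | 2 | 36.8% | 77.9% |
| 109 | 3 | 58.6% | 91.8% |
| 110 | 3 | 57.9% | 91.6% |
| 116 | 3 | 53.9% | 90.2% |
| 120 | 3 | 51.3% | 89.3% |

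At 110 the lower bound is 93.10% with three failures and 91.87% with four. Type I error is 0.046. Power is 70.4% at a true rate of 97.5% and 82.1% at 98%, and reaches 90% at about 98.4%. At 97% the expected number of failures is 110 × 0.03 = 3.3, with 3 allowed. At that rate exact power first reaches 90% at n = 257 and holds at every n only from 292.

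**Step 3: which safety rate was meant?** The 5.5-point margin fits only one of them: 98.5 − 5.5 = 93.0, whereas 97 − 5.5 = 91.5. That points to 98.5%. But 3.2 also says that a 3% event rate is expected, which is 97%, immediately before it uses 98.5%. Every event rate in Table 2 (2.1% to 5.3%) is above the 1.5% that 98.5% implies.

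**The case against.** The strongest reply is that little depends on this. Section 8.8 says openly that it used a normal approximation, and 85 is correct under that method. The study enrols 110 or more, so 85 decides nothing. At 110 the switch to the exact rule does no harm: safety power at 98.5% is 91.6% exact against about 90.2% by z test, and efficacy is 95.5%. The 97% looks like the neighbouring column of the 8.1 table copied by mistake, in which case 57.9% describes a design that nobody sized for. The 120 is a ceiling, and the shortfall there is at most 0.7 points.

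Most of this stands, and it keeps the point modest. Two things remain. A figure presented as the minimum for 90% power does not deliver 90% under the test that will be used. And the misprint reading, though likely, is not settled by the text, because 3.2 calls both 3% events and 98.5% freedom from events expected.

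The drop to 77.9% with 108 evaluable subjects is only a caution and may never arise. Subjects without evidence of an event count as successes (8.2; SAP 5.6.1), ITT Failure subjects with the catheter inserted are added to the safety set, and enrolment may run to 120.

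**Conclusion.** The concern holds. The efficacy minimum of 85 gives 83.3% power under the planned test. The safety minimum of 110 is inconsistent with the 97% in 8.8 and consistent with the 98.5% in 3.2 and 8.1.

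If 98.5% is confirmed, the promise of 90% in 6.4.1 is kept at 110 for both endpoints. For safety it slips just under 90% from 117 to 120. If 97% is intended, safety power is 57.9% at 110 and 51.3% at 120, and the trial is too small for its stated power. Type I error is controlled in either case.

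These figures assume independent subjects, no missing outcomes, and a safety set of the size shown. The section should be corrected, but the error does not by itself invalidate the design.

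**What to change.** 1. State one planning rate for safety and use it in 3.2, 8.1 and 8.8, including the sentence in 3.2 that expects a 3% event rate.
2. Recompute 8.8 with the Clopper-Pearson rule. Replace 85 with 86 (the first n to reach 90%), or with 93 if 90% is to hold at every larger n, and say which criterion was used.
3. Give allowed failures and exact power at 110 and 120 for both endpoints. At 98.5% for safety and 93.7% for efficacy these are: safety 3 failures, 91.6% and 89.3%; efficacy 11 and 12 failures, 95.5% and 96.0%.
4. Reconcile the maximum of 110 in 3.2 with the 120 in the synopsis, 6.4.1 and 8.8. The 110 in 3.2 carries an asterisk whose note is not visible in the text available, so check that note first.

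The cost is a text and table change in protocol 3.2, 8.1 and 8.8, possibly with the approval steps of protocol 11.17.2. The SAP body has no sample-size section to edit. Some stated figures become slightly less favourable. No subjects are added if 98.5% is confirmed. If 97% is intended, the sample size itself must be reconsidered.
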